**Study documents**

**Scientific background:** Morbid obesity, defined as a body mass index (BMI) of  $\geq 40$  kg/m^2 (class III obesity), is a chronic disease with life-threatening cardiometabolic consequences such as elevated blood pressure (systolic [SBP] or diastolic BP [DBP]), fasting plasma glucose (FPG), triglycerides (Tg), and low high-density lipoprotein cholesterol (HDL-c), all summarised as metabolic syndrome (MetS) (Baffi, Wood et al. 2016), increasing substantially the rates of total mortality, with most of the excess deaths due to heart disease, cancer, diabetes, and important life expectancy reductions in compared with normal weight (Kitahara, Flint et al. 2014). Moreover, morbid obesity has been associated with impairments of cardiorespiratory fitness and muscle strength, limiting the capacity to perform activities of daily living (Pazzianotto-Forti, Moreno et al. 2020) Additionally, this fact increases the economic costs associated with healthcare in this population (Espallardo, Busutil et al. 2017).

Due to the multi-factorial aetiology of morbid obesity, such as the genetic load (e.g. the *FTO* gen), and other environmental factors, including mainly lifestyle determinants such as physical activity/exercise training participation, and diet as main modulators, the application of lifestyle strategies have been proposed prior to alternative surgical intervention in these populations (Bächler, Papamargaritis et al. 2013, Espallardo, Busutil et al. 2017). In this sense, exercise training as the resistance training (RT), defined as any exercise that causes voluntary skeletal muscle contraction by using external weights

including dumbbells and metal bars (Schoenfeld, Grgic et al. 2017), is a known non-pharmacotherapy strategy for improving muscle strength and functional capacity in obese patients undergoing bariatric surgery (Huck 2015). Similarly, high intensity interval training (HIIT), defined as several and brief bouts of high-intensity effort usually by cycling/running, interspersed by recovery periods (Gibala, Little et al. 2012, Delgado-Floody, Izquierdo et al. 2020), has produced strong evidence for the improvement of cardiometabolic risk factors for type 2 diabetes mellitus, arterial hypertension, central arterial stiffness, vascular function, and cardiorespiratory fitness (Ramírez-Vélez, Hernández-Quiñones et al. 2019). Thus, HIIT might have protective effects against the development of cardiometabolic diseases including populations with poor glucose control and high blood pressure in comparison to moderate-intensity continuous training (MICT) (Campbell, Kraus et al. 2019). Thus, following RT or HIIT alone, there have been described unique physiological adaptations for improving for example muscle strength, the endurance performance by walking test, as well as beneficial metabolic improvements at MetS markers including fasting glucose reductions, increases at HDL-c, and decreases in Tg in populations with higher adiposity.

Thus, in individuals with morbid obesity for example, exercise training has proven to be effective for inducing clinically significant weight loss (5–10%) (Gerber, Anderin et al. 2015), and for the reduction of cardiovascular risk (Delgado-Floody, Alvarez et al. 2019), in accordance with the standard recommendations for these cohorts prior to bariatric surgical. Additionally, there are also other benefits such as the increase of skeletal muscle mass, the reduction of body fat, and better glucose control by the lowering of fasting plasma glucose (FPG), and lipids regulation (i.e., increases of HDL-c, and decreases of Tg) (Han and Lean 2016). Briefly, 12 weeks of concurrent training (CT), defined as a combination of both MICT / plus RT, decreased body weight (by ~7.3

kg), blood pressure, and FPG in this cohort (Marc-Hernández, Ruiz-Tovar et al. 2019).

In addition, part of our preliminary findings have shown that 20 weeks of RT decreases MetS risk factors in morbidly obese patients, showing a low inter-individual variability those patients with greater adiposity, revealing that with more adiposity alteration, the benefits of RT are also more visible (Delgado-Floody, Alvarez et al. 2019). However, some inconsistencies have been described after CT, that are directly related with the 'order' (i.e. starting the CT session with MICT followed by RT, or vice versa) of the CT session. For example, some literature reports that by starting the exercise session with RT, participants can get more benefits and improve their physical fitness markers (i.e. increases of upper body strength and neuromuscular markers) (Murlasits, Kneffel et al. 2018). However, in contrast, other studies have reported that starting CT with MICT/or HIIT does not alter physiological adaptations in similar outcomes (Wilhelm, Rech et al. 2014). Other evidence shows that starting CT with firstly RT exercises clearly promotes greater lower-body strength gains and neuromuscular economy (Cadore, Izquierdo et al. 2013). By contrast, other reports claim no more benefits by starting with MICT/HIIT or RT to physical fitness markers in populations of athletes (Eddens, van Someren et al. 2018), and additionally, no additional benefits for decreasing body fat using one or another exercise modality when starting the CT session (Cadore, Izquierdo et al. 2012). However, little is known about the interindividual variability of exercise training (IVET) in relation to different order session of CT in morbidly obese populations, and in health-related outcomes, such as MetS markers. Briefly, IVET means that some subjects achieve benefits after training, and are termed responders (Rs), while others exhibit a worsened or unchanged response, that are commonly known as nonresponders (NRs) (Bouchard, Blair et al. 2012). With regard to the causes of IVET, genetic (Stephens, Xie et al. 2015), and environmental factors including the mode of exercise training (Alvarez, Ramirez-

Campillo et al. 2017), have been described. In addition, considering the health-related benefits of CT including MICT/or HIIT plus RT in terms of physical fitness, and the metabolic markers in different populations, as well as taking into account the previous discrepancies of the order session in relevant literature, it is necessary to investigate the exercise modalities interaction as a precision medicine for improving MetS markers. This study will follow the CONSORT guidelines for randomised trials, will be developed in accordance with the Declaration of Helsinki (2013), and has been approved by the Ethical Committee of the Universidad de La Frontera, Temuco, Chile (DI18-0043 Project).

**Design:** An experimental, and randomized control clinical study. **Methods:** This study is a parallel-group randomised controlled trial in which 43 women with morbid obesity that will be randomly allocated to one of the two similar CT exercise programmes. The exercises will be applied in different session order by the two groups (HIIT+RT,  $n=17$ ), and resistance training plus high-intensity interval training (RT+HIIT,  $n=17$ ). All volunteers will read and signed an informed consent. The inclusion criteria will be; (i) being a candidate for bariatric surgery, (ii) aged between 18 and 60 years, (iii) being medically authorised, and (iii) with a body mass index (BMI)  $\geq 40$  kg/m^2 or  $\geq 35$  kg/m^2 with additional comorbidities (i.e. diabetes, hypertension, insulin resistance) controlled by pharmacotherapy according to the Chilean requirements for morbidly obese patients in order to be a candidate for bariatric surgery. The exclusion criteria will be; (i) having physical limitations preventing the performance of exercise (e.g. restricting injuries of the musculoskeletal system), (ii) having exercise-related dyspnoea or respiratory alterations, (iii) having chronic heart disease with any worsening in the last month, and (iv) adhering to less than 80% of the total interventions (these results were excluded from the statistical analyses).

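### Women enter at BMI ≥40 or at BMI ≥35 with drug-controlled comorbidity, and the protocol links response to adiposity, but no between-arm analysis uses baseline BMI or entry route; this costs precision and leaves any imbalance uncorrected

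*Combined protocol and SAP*

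**What the plan says.** The Scientific background opens with "Morbid obesity, defined as a body mass index (BMI) of" 40 kg/m² or more, and labels this class III obesity. The Design and Methods text calls all participants women with morbid obesity: "43 women with morbid obesity that will be randomly allocated to one of the two similar CT exercise programmes". Its inclusion criteria offer two routes: BMI ≥40, or BMI ≥35 "with additional comorbidities (i.e. diabetes, hypertension, insulin resistance) controlled by pharmacotherapy according to the Chilean requirements for morbidly obese patients".

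The background also reports the investigators' preliminary findings after 20 weeks of RT. Variability was low in patients with greater adiposity, "revealing that with more adiposity alteration, the benefits of RT are also more visible".

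Allocation is described only as random; no stratification, blocking or minimisation is mentioned. In the SAP, the main metabolic syndrome markers (waist circumference, systolic and diastolic pressure, fasting glucose, HDL and triglycerides) are tested by the time-by-group interaction in a two-way repeated-measures ANOVA. Non-responder percentages are compared between arms by chi-square. No model is given a term for BMI, entry route or medication. An ANCOVA is mentioned only as the source of partial eta squared, with no covariate named. A baseline t test is planned, with no variables listed and no action attached.

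**The concern.** The eligibility rule itself creates a mixture of BMI ranges, and the protocol's only statement about who responds more concerns adiposity. An analysis that ignores baseline adiposity leaves explainable variation in the error term. It also has no way to correct the comparison if one arm receives more lower-BMI women. Both matter more in arms of 17 than in a large trial, because sizeable imbalances are then common and precision is scarce.

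There is also a question of wording. Women entering at BMI 35 to below 40 do not meet the background's definition of morbid obesity. A conclusion stated for morbid obesity in that sense would not describe everyone studied.

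**Working it through.** **Inputs from the documents.** Two arms of 17 (Design and Methods), so 34 women; alpha 0.05 (SAP; two-sided assumed). The stated total of 43 does not match 17 + 17 = 34. That is a separate matter, and 17 per arm is used here. The documents give no sample-size calculation, so there is no figure of the plan's own to reproduce on this point.

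**Assumptions, not in the documents.** The share *p* of women entering at BMI 35 to below 40 is taken as 20–50%. The difference *b* between routes in mean change on a marker is taken as 0.5–1.0 residual SD.

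**Step 1: how often the arms are uneven.** Let the number of lower-BMI entrants be Binomial(34, *p*), split hypergeometrically 17/17. The probability that the arms differ by at least 4 such women (4/17 = 23.5 percentage points) is:

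| *p* | Probability |
|---|---|
| 0.2 | 0.130 |
| 0.3 | 0.189 |
| 0.4 | 0.220 |
| 0.5 | 0.229 |

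**Step 2: what that does to the estimate.** The shift in the between-arm difference is imbalance × *b*: 0.235 × 0.5 = 0.12 SD to 0.235 × 1.0 = 0.24 SD. For scale, the standard error of the difference with residual SD 1 is √(2/17) = 0.34 SD.

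**Step 3: false-positive rate.** With two time points, the time-by-group test is equivalent to a t test on change. In 100,000 simulated trials per setting with no order effect (change = *b* × route + N(0,1), 17 per arm, share 30% or 50%), the rejection rates were:

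| | Unadjusted | Adjusted for route |
|---|---|---|
| All allocations | 4.9–5.1% | 4.9–5.1% |
| Allocations ≥20 points apart | 6.3–10.9% | 4.8–5.1% |
| Allocations ≥30 points apart | 8.0–16.9% | 4.8–5.5% |

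Averaged over allocations, the error is nominal. The excess exists only conditional on an imbalance, and adjustment removes it to within simulation error.

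**Step 4: precision.** In the same model, adjusting for route reduced the mean standard error by about 1% (*b* = 0.5, 30% share) to 9% (*b* = 1.0, 50% share). By a normal approximation, 17 per arm gives 80% power only for (1.96 + 0.84) × √(2/17) ≈ 0.96 SD, and about 31% power for 0.5 SD. There is little precision to spare.

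**Step 5: non-responders.** If non-responder prevalence differed by 30–50 points between routes (assumed), a four-woman imbalance would shift the between-arm difference by 0.235 × 0.3 = 7 points to 0.235 × 0.5 = 12 points. That is 1.2 to 2 women of 17. The smallest uncorrected chi-square p value that a two-woman difference can give with 17 per arm is 0.145.

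**The case against.** The strongest reply is that randomisation and the p value already allow for chance imbalance. That stands for the women as randomised: Step 3 shows no overall inflation. A reader might infer that ignoring entry route makes a false claim of an order effect more likely than 5%, but neither the documents nor the arithmetic support this. Conditional error and lost precision remain. Separately, the plan drops women "adhering to less than 80% of the total interventions" from the analysis, so the analysed arms need not keep the balance that randomisation gives.

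A reader might also infer that the protocol says the two routes respond differently. It does not. It describes a trend with adiposity after RT alone, not a step at BMI 40 and not a result for concurrent training. Nor does entry route separate treated from untreated women: drug-controlled comorbidity is required on one route and not excluded on the other. Entry route is therefore a crude proxy, and this favours continuous baseline BMI as the covariate.

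A third inference, that an imbalance could by itself produce a significant non-responder difference, fails on Step 5.

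Finally, the wider criterion is disclosed in full and tied to national requirements for bariatric candidates. That explains the criterion but leaves the background definition unreconciled. The ANCOVA and baseline t test do not answer the point. No covariate is named, and a split of 7/17 against 3/17 gives a Fisher p of 0.26, so a significance test at baseline would probably miss it.

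**Conclusion.** The point holds as a low-cost improvement, not as a defect of validity. The between-arm analyses omit a baseline characteristic that the eligibility rule makes heterogeneous and that the protocol links to response. Under the assumed shares and effects, adjustment is worth about 1–9% of the standard error. It would also correct an imbalance of four or more women, which arises in 13–23% of allocations and would shift a marker's between-arm difference by at least 0.12–0.24 SD. If the true route effect or the lower-BMI share is smaller than assumed, the gain shrinks towards nothing; the documents give neither figure. The mismatch between the definition and the inclusion criterion is one of wording and needs reconciling.

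**What to change.** 1. In the between-arm model for each metabolic syndrome marker, prespecify baseline BMI (continuous, already needed for eligibility) as a covariate, or entry route if a category is preferred. In the repeated-measures form the term must interact with time, since a main effect alone leaves the time-by-group estimate unchanged. A model of change with arm and BMI does the same job.
2. Report non-responder counts by arm and entry route, descriptively.
3. Stratify the allocation list by entry route only if allocation has not been done. The SAP reports in the past tense which outcomes in each arm were analysed by Wilcoxon test, so this may be too late.
4. Reconcile the background definition with the inclusion criterion. Word the conclusion for the women enrolled: candidates for bariatric surgery with BMI ≥40, or ≥35 with treated comorbidity.

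The cost is one degree of freedom per model, a small loss of precision if BMI turns out to be unrelated to change, and a slightly longer population statement. No extra patients, visits or measurements are needed.

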**Statistical Analysis Plan (SAP):** We will apply 2 main forms of statistical analyses a) to report the pre-post changes in mean terms, and b) to report the results according with the inter-individual responses based on the technical error criteria, where according with the error calculated in the three previous measurements registered by the sample that was voluntary. Graph pad Prisma statistical software 8.0 (San Diego, CA, USA) will be used. The normal distribution of all the variables were tested using the Shapiro-Wilk test. Data will be presented as the mean and (95%CI) in tables, as mean

with ( $\pm$ ) standard error in Figures 1, 2, and 3, and as individual delta in Figure 4 for identification of Rs and NRs. Normality and homoscedasticity assumptions for all data were analysed using the Shapiro–Wilk and Levene’s test, respectively. In the HIIT+RT group, the Tg outcome, as well as in the RT+HIIT group, LDL-c, and lean mass outcomes were analysed by the *Wilcoxon* non-parametric test. For training-induced changes, the student’s *t* test was used to identify differences at baseline, while a repeated measure two-way ANOVA was applied to assess the occurrence of an actual training effect; namely,  $p < 0.05$  for the interaction (time x group) on the main MetS (WC, SBP, DBP, FPG, HDL, and Tg, as well as to the secondary outcomes). A Sidack’s post hoc test was used for multiple comparisons. Additionally, the Eta partial squared for interaction (Time x Group) was assessed by  $\eta^2$  obtained from the ANCOVA with small ( $\eta^2=0.01$ ), medium ( $\eta^2=0.06$ ), and large ( $\eta^2=0.14$ ) effects defined according to (Lakens, 2013). The prevalence of NRs was described using the comparisons by percentage between both experimental groups using a Chi square test  $\chi^2$ . All statistical analyses were performed with SPSS statistical software version 23.0 (SPSSTM Inc., Chicago, IL). The alpha level was set at  $p < 0.05$  for statistical significance.

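### Randomised women below 80% adherence are dropped from the only analyses planned, and 43 allocated does not match arms of 17 and 17

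*Combined protocol and SAP*

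**What the plan says.** The Design/Methods paragraph of the protocol describes a parallel-group trial in which "43 women with morbid obesity that will be randomly allocated to one of the two similar CT exercise programmes". The two arms perform the same training components and differ only in sequence: "The exercises will be applied in different session order by the two groups". Each arm is given as n=17.

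The fourth exclusion criterion in that paragraph is "adhering to less than 80% of the total interventions (these results were excluded from the statistical analyses". The same part of the document states: "This study will follow the CONSORT guidelines for randomised trials".

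The Statistical Analysis Plan sets out two main analyses. The first is "to report the pre-post changes in mean terms", for which "a repeated measure two-way ANOVA was applied to assess the occurrence of an actual training effect" through the time-by-group interaction. The second classifies individual responses: "The prevalence of NRs was described using the comparisons by percentage between both experimental groups", with a chi-square test. The SAP names no analysis population for either. It has no sensitivity analysis and no rule for missing post-training values.

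**The concern.** There are two separate defects.

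**Analysis set.** Although it is listed with the eligibility criteria, the adherence rule can be applied only after a woman has been allocated and exposed to her session order. It takes her results out of the statistical analyses in general, not out of one secondary analysis. As nothing in the SAP offsets it, the trial has in effect only a per-protocol analysis. If session order influences adherence, and adherence is related to change, the retained groups are no longer comparable by randomisation, and that comparison is the trial's question. Even with equal adherence in both arms, dropping women who probably change less raises the mean pre-post change and lowers the non-responder percentage, the two results the SAP sets out to report. The rule gives a threshold and a reference total, but not how adherence is counted (sessions attended, sessions completed or work achieved), and each choice could exclude different women.

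**Counts.** The number allocated and the two arm sizes cannot both be the randomised numbers, so the denominator of an all-randomised analysis is unclear.

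**Working it through.** **Counts (all inputs from Design/Methods).** 17 + 17 = 34; 43 − 34 = 9; 9/43 = 20.9%. The stated 43 is not reproduced from the arm sizes. As a dropout allowance, 34/(1 − 0.20) = 42.5, rounded up to 43, so a 20% allowance would fit, but none is stated. The text available gives no power, effect size or SD, so no sample-size calculation can be reproduced.

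**Assumptions for the illustrations.** The documents give neither the excluded fraction f nor the correlation r between adherence and change. I take r = 0.3 to 0.5, f = 5%, 10% or 20.9% (the last only if all 9 women were low adherers), bivariate normality, unit-variance change and no true order effect.

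**Pre-post change, equal exclusion in both arms.** The mean among retained women is overstated by r × φ(q)/(1 − f), where q = Φ⁻¹(f). For f = 0.10, φ(q) = 0.1755 and 0.1755/0.90 = 0.195; multiplying by 0.3 and 0.5 gives 0.058 and 0.097 SD.

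**Non-responder percentage.** The retained rate is [P(NR) − P(NR and excluded)]/(1 − f), with an assumed true rate of 40%.

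| Excluded f | Mean change overstated, r=0.3 / r=0.5 | 40% non-responders reads as, r=0.3 / r=0.5 |
|---|---|---|
| 5% | 0.033 / 0.054 SD | not tabulated |
| 10% | 0.058 / 0.097 SD | 37.6% / 36.0% |
| 20.9% | 0.109 / 0.182 SD | 35.6% / 32.5% |

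**Between-arm test.** These figures come from simulation of 100,000 trials per scenario, with a two-sided 5% t test on change, which equals the time-by-group test when there are two time points.

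| Scenario | Bias, r=0.3 / r=0.5 | Type I error, r=0.3 / r=0.5 |
|---|---|---|
| 21/22 start, one threshold, equal adherence | none | 5.0% / 5.0% |
| 21/22 start, 17 highest adherers kept per arm | 0.02 / 0.03 SD | 5.2% / 5.9% |
| 21/22 start, 10% v 32% excluded | 0.10 / 0.17 SD | 5.9% / 7.6% |
| 19/24 start, 17 highest adherers kept per arm | 0.08 / 0.14 SD | 5.9% / 7.6% |
| 17/26 start, 17 highest adherers kept per arm | 0.17 / 0.28 SD | 7.8% / 13.1% |

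In the 10% v 32% case the expected loss is 0.10 × 21 + 0.32 × 22 = 9.1 women, close to the gap of 9. The last row is the extreme, with all 9 taken from one arm.

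**Precision.** Assuming 80% power and a two-sided 5% test (the documents state neither power nor sidedness), the detectable difference in change is 0.99 SD with 17 + 17 and 0.88 SD with 21 + 22.

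**The case against.** The strongest reply is that the larger figures depend on an imbalance that the documents do not show. With equal adherence the between-arm test is not inflated, and a near-equal 21/22 start moves it only slightly. The scenarios that keep exactly 17 per arm are not the plan's rule, which is a fixed 80% cut-off, and nothing in the protocol supports a 19/24 or 17/26 start. These points stand, so those rows show only what the rule could do.

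A second point also stands. The Type I error figures treat adherence as a marker of prognosis. If adherence itself causes change, an order that lowers adherence produces a real difference among all randomised women; the null is then false and those error rates do not apply. The adherence-selected analysis would still answer a different question from the randomised one.

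Third, an analysis of women who trained as intended is a legitimate question in exercise research, and the rule is at least written down. That justifies keeping it as a labelled secondary analysis, but not as the only one.

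Finally, 43 could be 34 plus a 20% allowance, or the arm sentence could simply be garbled. Either is possible. The mismatch is a count to reconcile and adds no evidence of bias.

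**Conclusion.** Both parts hold. As written, the plan yields only an adherence-selected comparison, and the number allocated contradicts the arm sizes by 9 women (20.9%). These two facts come directly from the text and do not depend on the illustrations.

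The size of the effect is uncertain. No adherence data by arm are given, so this is a risk the plan leaves uncontrolled, not a demonstrated bias. With 5% to 20.9% excluded it is modest for mean change (0.03 to 0.18 SD), and it is zero for the between-arm test when exclusion is equal. It becomes material if exclusion differs by arm. All these magnitudes rest on the assumed r and f and shrink to zero as exclusions do. The point must be fixed because no planned analysis preserves the randomised comparison.

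**What to change.** 1. Remove the adherence rule from the exclusion criteria.
2. State in the SAP that both main analyses include every randomised woman in her allocated arm, whatever her adherence. The SAP does not name a single primary analysis, so the wording should cover both.
3. Seek post-training measurements from all women where they can still be obtained.
4. For the mean changes, handle missing post values with a likelihood-based mixed model or with multiple imputation that includes baseline value, arm and adherence. For the non-responder percentages use multiple imputation, because a mixed model does not classify individuals, and keep the all-randomised denominator.
5. Define how adherence is counted, and keep the set at 80% or above as a labelled sensitivity analysis.
6. Reconcile 43 with 17 + 17, stating which count is recruited, randomised and analysed, and provide for reporting exclusions with reasons by arm.

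**Cost.** This needs rewording in the protocol and SAP, plus post-tests for low adherers. The estimated training effect may be somewhat diluted. The past tense in the exclusion rule and the SAP suggests that follow-up may be complete. If low adherers have no post-tests, the result will rest more on the missing-data model, which would extrapolate from women at or above 80% adherence to those below it in a small sample. That limitation should be stated.
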